USC also has an MTOP conference but about one-third of patients are discussed after therapy has been determined by the referring physician. However, the pulmonary division has established a solitary pulmonary nodule clinic specifically designed to identify patients with early stage lung cancer who then rapidly progress to diagnostic evaluation and treatment recommendations. There are 2 clinic sessions per month and 15 patients evaluated in each clinic. The USC site investigator and RA will have access to the nodule clinic schedule and determine potential patient eligibility prior to clinic. As with the MTOP clinics above, the RA will attend the nodule clinic, the appropriate clinicians will be approached to confirm patient's study eligibility and to obtain permission to approach the patient. We will also intensify recruitment at thoracic surgery offices in an effort to capture the patients treated prior to MTOP and not seen in solitary nodule clinic. Note that none of the participating sites use formal communication protocols that define minimum information delivery or ascertainment of patient comprehension.

All 4 study sites are referral centers for lung cancer treatment with large catchment areas. We surveyed the lung cancer physicians and coordinators at all 4 centers regarding a potential diffusion effect between study patients and controls. Because of widespread geographic distribution of patients and MTOP scheduling sequences during visits the possibility of intervention and control patients meeting and discussing variations in communication is remote. To further ensure against a diffusion effect, we will alternate control and intervention recruitment dates as part of the randomization scheme.

In our cohort study, 80% of the patients enrolled identified a pulmonologist, thoracic surgeon, or oncologist as the individual who told them the most about lung cancer. These specialists

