The main outcome of interest is whether patients undergo surgery is a dichotomous variable, either yes or no. We will compute proportions to estimate the probability of surgery for blacks and whites and compute 95% confidence intervals for the proportions. Since the main outcome is dichotomous, logistic regression for clustered data (clustered within sites) using multiple predictors will be used to assess the simultaneous effect of predictors on the outcome.

Specific Aim 1. To maximize surgical rates for all patients with stage I and II, non-small cell lung cancer who do not have absolute contraindications for lung resection surgery.

hypothesis 1a. a cancer communicator who utilizes active listening and teach-back methods during discussions about lung cancer surgery with newly diagnosed, early stage patients will increase the rate of surgery in Caucasian and African-American patients who do not suffer absolute contra-indications for lung cancer surgery compared to usual care

The primary outcome variable, surgery yes or no, will be compared in the control group randomized to usual care, to the intervention group randomized to the cancer communicator. Bivariate analyses will be performed using the surgical outcome as the dependent variable. Independent variables in these analyses will include important group, demographic variables

such as age, race, marital status, household income, health insurance, gender, and education as well as measures of trust, patient satisfaction, functional status, self-reported health, comorbid illness, perceptions of communication, and the communication intervention. We will use bivariate analyses, including correlations and chi-square tests of association, to make preliminary assessments of the relationships between study variables, overall and by race.

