The modeling approach will be to initially define as large a maximum model as possible using main effects only (initially no interactions). Preliminary analyses of similar data indicates that the sample size combined with a sufficient number of events (surgery yes) will allow upwards of 30-35 main effects to be included in the model with good reliability for estimation and inference. The generalized estimating equations (GEE) for binary outcomes will be used to fit logistic regression models for clustered data [102]. The primary outcome variable is binary, surgery yes or no, and outcomes of patients clustered within the same site (and/or MD) are expected to be correlated. GEE will allow fitting a logistic regression to the binary outcome while adjusting for the effect of clustering within the same site (and/or MD). As stated previously, independent variables in these analyses will include important demographic variables such as age, race, marital status, household income, health insurance, gender, and education as well as measures of trust, patient satisfaction, functional status, self-reported health, comorbid illness, perceptions of communication, and the communication intervention. The significance of each of the main effects while adjusting for all other effects from the maximum model will be assessed. A backwards elimination approach will, initially, remove effects with a p-value of greater than 0.10. This excludes selected predictors forced predictors into the model (forced predictors include group, comorbid illnesses and selected baseline scores). The reduced model will be refit. Variables have p-values greater than 0.05 will then be removed. The final reduced main effects model, including forced predictors will be refit. Selected interactions will be considered for inclusion into the final reduced main effects model. For the secondary outcomes, survival analysis techniques will be used to assess the one year, post-enrollment survival in surgical and non-surgical groups. Kaplan-Meier curves will be generated. Linear regression models for repeated measures (discrete) outcomes using GEE will be used to assess patient satisfaction of patients that received interventions compared to those who did not, for patients' perceptions of communication for those patients that received intervention compared to those who did not, and for SF12 scores at 6 months post-enrollment and 12 months post enrollment. Covariates will include baseline, group, and other covariates listed above.

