
hypothesis 1b. the communication intervention will be more effective in patients who score lower in measures of health literacy

Using the logistic regression analyses for clustered data as noted above, the interaction effects of health literacy, S-TOFHLA scores, and intervention group will be tested in all models. . S-TOFHLA scores will be tested as a continuous variable and also, separately, as a dichotomous variable comparing those categorized as inadequate or marginal literacy with those categorized as adequate literacy [103]. Cumulative pre-intervention surgical rates will be compared at all sites with post-intervention rates using Pearson's chi-square test. Post-intervention rates will be compared using test of proportions and changes in proportions from baseline will be compared between surgical and nonsurgical groups using appropriate methods. To determine if the post-intervention rate approaches maximal surgical rates, we will identify patients with high risk co-morbidities, above the age of 80, and need for pneumonectomy or multiple lobectomy in the "no surgery group", subtract this sum from the denominator then re-calculate the surgical rate. We will analyze the secondary specific aim, To measure the effect of the intervention on patients' perceptions of communication and satisfaction with care, by dichotomizing these variables and replacing surgery as the dependent variable in chi-square and logistic regression models as described under the specific aim above.

Specific Aim 2. To reduce the documented difference in lung resection surgery and mortality between African-American and White patients with early stage, non-small cell

lung cancer.

hypothesis 2a. giving physicians who make lung cancer surgery decisions data relating co-morbidity to surgical outcomes will reduce racial differences in surgery

hypothesis 2b. using a real time lung cancer registry to provide physicians race-specific feedback about their surgical treatment of early stage lung cancer patients will reduce racial differences in surgery

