The SF-12 physical and mental component scores will be converted to 0 – 100 scales and utilized as the dependent variable. Baseline scores will be compared first to 6 month scores then 12 month scores using paired t-tests. Generalized linear mixed models for repeated measures data will be constructed in a similar manner as the logistic regression models described above; however, surgical status, race, and comorbid conditions will be forced predictors in these model.

Note that interim analyses regarding specific aims 1 and 2 will be performed at the end of study year 2 then annually. If statistically significant benefits in care are documented on surgical rates and reduction in disparities, the study will be terminated and workshops and individual training sessions of the communication methodologies will be initiated for the care teams at all the study sites.

7. Sample Size

Power computations are computed for post-intervention comparison of proportions. The project anticipates enrolling 496 patients into the study due to constraints on budget, patient availability, and study duration. Thus, we compute the minimal effect size we can detect with statistical power of 80% for our primary aim, AIM 1, using the specified sample size. In computing the effect size, we specify our main outcome as the probability of undergoing surgery for all patients post-baseline as compared to the probability for all patients in the previous study because all groups will receive the data registry and feedback interventions.

Let p_1 be the proportion all patients who undergo surgery in the present study and $p_0 = 0.63$ be the proportion of patients who underwent surgery in the previous study. Using a one-sample test of proportion with 496 subjects overall and significance level of 0.05, we have 80% power to detect a minimally important difference (increase) in surgical rate of $p_0 = 0.63$ to $p_1 = 0.69$. With a sample size of 159 for blacks, we have 80% power to detect an overall increase from $p_0 = 0.55$ (as measured in the previous study) to $p_1 = 0.66$ with significance level of 0.05. With a sample size of 337 for whites, we have 80% power to detect an overall increase from $p_0 = 0.66$ (as measured in the previous study) to $p_1 = 0.73$ with significance level of 0.05.

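### The 80% power claimed for Aim 1 is for all 496 patients pooled against a fixed 0.63; the randomised communicator comparison has no stated power or detectable difference

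*SAP*

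**What the plan says.** SAP section 7 takes 496 patients as fixed by budget, patient availability and study duration. It then sets out to give "the minimal effect size we can detect with statistical power of 80% for our primary aim, AIM 1". The comparison is the surgery rate in all patients of the present study against that of "all patients in the previous study because all groups will receive the data registry and feedback interventions". The result is stated as: "Using a one-sample test of proportion with 496 subjects overall and significance level of 0.05, we have 80% power to detect" an increase from 0.63 to 0.69, which the SAP calls the minimally important difference. The two race-specific statements have the same form: 159 black patients against 0.55 (detecting 0.66) and 337 white patients against 0.66 (detecting 0.73). Section 7 ends with a remark that clustering was negligible in the previous study. There is no other power statement.

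Aim 1 is worded broadly: "To maximize surgical rates for all patients with stage I and II" disease and no absolute contraindication. Its first hypothesis, 1a, is that the communicator raises surgery rates relative to usual care. SAP section 6 says that the primary outcome "will be compared in the control group randomized to usual care, to the intervention group randomized to the cancer communicator". The planned model is logistic regression fitted by GEE: "GEE will allow fitting a logistic regression to the binary outcome while adjusting for the effect of clustering within the same site" and/or physician. The Aim 1 text also contains a before/after analysis: "Cumulative pre-intervention surgical rates will be compared at all sites with post-intervention rates using" Pearson's chi-square test.

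On allocation, Protocol section E says that patients are randomised to one of the two arms, without giving a ratio. Protocol section E.2 adds: "we will alternate control and intervention recruitment dates as part of the randomization scheme".

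**The concern.** The power figure and the randomised hypothesis concern different contrasts. A one-sample test of 496 pooled patients against a constant asks whether surgery is now more frequent than in the previous study. Hypothesis 1a asks whether surgery is more frequent with the communicator than without. Every patient in both arms is exposed to the registry and feedback, so a pooled rise can occur with no communicator effect at all.

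A reader who takes section 7 at its word will think that the trial can detect about 6 points on its primary aim. For the randomised comparison that is far too optimistic. The practical risk lies in interpretation: a non-significant arm difference could be read as evidence against the communicator from an adequately powered trial, when the data could not exclude an effect of the size section 7 mentions.

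**Working it through.** **Inputs from the documents.** Total 496; previous-study rates 0.63 (all), 0.55 (black patients) and 0.66 (white patients); target rates 0.69, 0.66 and 0.73; subgroup sizes 159 and 337 (all SAP section 7); two-sided 0.05 (SAP section 6).

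**Assumptions, because the documents give no figure.** Individual 1:1 allocation (248 per arm); usual-care rate 0.63, varied below. The arm figures are unadjusted and for a single look.

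**1. Section 7's own figures.** One-sample normal approximation:

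power = Φ{ [p1 − p0 − 1.96·√(p0(1−p0)/n)] / √(p1(1−p1)/n) }

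For n = 496, 0.63 v 0.69: the standard errors are √(0.2331/496) = 0.02168 and √(0.2139/496) = 0.02077. So (0.06 − 0.04249)/0.02077 = 0.843 and Φ = 80.0% (exact binomial 80.2%). A one-sided test would give 87.9%, so the stated figure is two-sided. The other two give 80.8% (159, 0.55 v 0.66) and 78.9% (337, 0.66 v 0.73). Section 7 reproduces.

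**2. The randomised comparison.** Two-sample z test with pooled variance under the null, n per arm, p̄ the mean of p0 and p1:

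power = Φ{ [p1 − p0 − 1.96·√(2p̄(1−p̄)/n)] / √((p0(1−p0) + p1(1−p1))/n) }

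- 0.63 v 0.69, n = 248: p̄ = 0.66, standard errors 0.04254 and 0.04246; (0.06 − 0.08338)/0.04246 = −0.551; power **29.1%** (simulation with 400,000 runs: 29.4%).
- Solving for 80% gives p1 = 0.7463, a difference of **11.6 points** (simulation at that value: 80.1%).

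**3. Sensitivity to the usual-care rate (248 per arm).**

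| Usual-care rate | Detectable at 80% (points) | Power for 6 points |
|---|---|---|
| 0.55 | 12.2 | 27.2% |
| 0.63 | 11.6 | 29.1% |
| 0.69 | 10.9 | 31.8% |
| 0.71 | 10.7 | 33.1% |
| 0.75 | 10.0 | 36.4% |

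The 0.71 row is the case-weighted registry rate from the table in Protocol section C: (63×70 + 141×69 + 57×74 + 66×75)/327 = 71.3%. The protocol itself calls those rates overestimates.

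**4. Sensitivity to allocation (usual care 0.63).** Splits from 40:60 to 60:40 give 11.6 to 11.9 points, and 28% to 29% power for 6 points. If allocation is by recruitment date, an assumed design effect of 1.05, 1.10 or 1.20 gives 11.9, 12.2 or 12.7 points, and 28.0%, 26.9% or 25.1% power.

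**5. What the pooled test can and cannot see.** Hold the pooled rate at 0.69 and vary the split between arms:

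| Usual care v communicator | Section 7's pooled test | Arm comparison |
|---|---|---|
| 0.69 v 0.69 | 80.0% | 5.0% |
| 0.66 v 0.72 | 80.1% | 30.3% |
| 0.63 v 0.75 | 80.2% | 82.6% |

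The pooled test's power is the same whether the communicator effect is 0 or 12 points.

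**6. A null arm result.** If the observed arm difference is zero with both rates at 0.63, the 95% half-width is 1.96·√(2×0.63×0.37/248) = 8.5 points. With both at 0.69 it is 1.96·√(2×0.69×0.31/248) = 8.1 points. Either interval contains 6 points.

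**The case against.** The strongest reply is that section 7 hides nothing. It says that the comparison is with the previous study, gives the reason and names a one-sample test. Aim 1 is worded for all patients, and the Aim 1 text does plan a before/after comparison. That is fair, and the pooled calculation has a place there. The match is loose, though. The planned before/after test is a two-sample chi-square test on pre-intervention rates at the sites, for which the protocol describes a 2008–2009 chart review, whereas section 7 uses a different source and ignores its sampling error. Disclosure of the pooling also supplies no figure for hypothesis 1a.

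Second, the analysis plan does separate the communicator from the registry and feedback: by the randomised comparison, by comparing controls with historical rates (Protocol section E), and by an analysis limited to controls or with a communicator term (SAP, Aim 2). This stands. The planned inference on the communicator is not confounded; what is missing is its power.

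Third, 6 points is a pooled change, and the plan sets no target between arms. If usual care stayed at 0.63, a pooled 0.69 under 1:1 allocation would mean 2×0.69 − 0.63 = 0.75 with the communicator, where the arm test has 83% power. This also stands, so the 29% is illustrative and not a failure against a stated target. But it requires that registry, feedback and checklist do nothing in the control arm, which the plan does not assume.

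Fourth, the design-effect range is assumed. Section 7 reports correlations of −0.002 to 0.01. At 0.01, a design effect of 1.05 needs 6 patients per cluster (1 + 5×0.01) and 1.20 needs 21. At 165 patients a year over four sites, or about 0.8 per site per week, blocks of dates would be small. Those correlations appear to be for sites or physicians and not for dates, so they do not settle the matter. The conclusion does not depend on this range.

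**Conclusion.** The concern holds. Section 7's figures are correct for a pooled one-sample test against fixed historical rates, but that power does not belong to the randomised test of hypothesis 1a, and no other figure is given for it. Under 1:1 individual allocation, two-sided 0.05 and 0.63 under usual care, the detectable difference at 80% power is about 11.6 points, roughly twice the 6 points stated for the pooled rate. Usual-care rates of 0.55 to 0.75 move it only between 12.2 and 10.0 points, and power for 6 points stays between 27% and 36%. These figures ignore covariate adjustment in the GEE model and the interim analyses. The plan should be corrected on this point, but the correction concerns what is claimed and leaves the trial's conduct unchanged.

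**What to change.** In SAP section 7:

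1. Label 0.63 to 0.69, 0.55 to 0.66 and 0.66 to 0.73 as applying only to the pooled comparison with the previous study, with its rates taken as fixed. Say that they do not describe power for the communicator effect.
2. Add the detectable difference for the randomised comparison, with the allocation ratio and assumed usual-care rate. Suggested text:

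> As an unadjusted, single-look approximation, assuming 1:1 individual allocation (248 per arm), two-sided 0.05 and 0.63 surgery under usual care, there is 80% power for 0.63 to about 0.75 (11.6 points; about 12 down to 10 points for usual-care rates of 0.55 to 0.75) and, for illustration, about 29% power for a 6-point difference. This does not account for covariate adjustment in the GEE model or for the interim analyses.

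3. If allocation is by alternating recruitment date, say so and recompute on that basis.

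The cost is SAP wording and a less favourable stated figure: about 12 points between arms, beside 6 points for the pooled comparison. No extra patients are needed, and no test or estimate changes.

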C. Early Stage, Non-Small Cell, Lung Cancer Cases: The table below includes number of patients from 2007 with stage I and II, non-small cell lung cancer entered in each local cancer registry. These data only include patients with tissue proven diagnoses and not those who had CT lesions with extremely high cancer probability and refused surgery or dropped out of follow-up (we did include these patients in our prospective study). Therefore, eligible patients are underestimated while "percent surgery" rates are overestimated when factoring in all patients with early stage, non-small cell disease.

Site	Number of Cases	African-Americans	Percent Surgery
ECU	63	11	70
MCHS	141	24	69
UNC	57	14	74
USC	66	17	75

From our prospective study, we anticipate an average recruitment rate of 70% across sites. Only 11% of all patients approached during the post-diagnosis – pre-treatment recruiting interval refused participation and there was no difference by race.

D. Retrospective Chart Review: Our recently completed study demonstrated that co-morbid

conditions differentially affected black patients' care. Given these data, during the first six months of the intervention trial we will perform a retrospective chart review for the 2008 and 2009 calendar years. We will review all patients diagnosed with stage I or II, non-small cell cancer to serve as a baseline for surgical rates and to examine outcomes of patients treated with and without surgery using a very specific analysis of co-morbid conditions and severity. These data will be checked against Strand's report [45] to assess compatibility and level of detail. The results will be used by our expert panel of co-investigators and site investigators to create an educational checklist to remind lung cancer providers that surgical contra-indications are often relative and subjective. We anticipate the availability of approximately 100-150 charts per site in the 2-year pre-study window. Charts will be selected using appropriate ICD-9 billing codes. Data will be collected in an aggregate manner and no linkage files or specific patient identifiers will be maintained.

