Lung Cancer Surgery: Decisions Against Life Saving Care - The Intervention

NCT01687738

Protocol Date: May 13, 2011

Most Recent IRB Approval Date: March 29, 2016

Lung Cancer Surgery: Decisions Against Life Saving Care - The Intervention

STATISTICAL ANALYSES

Outcome Measures

Primary Outcome. Whether or not patients undergo lung resection surgery represents the main study outcome. We will conform to the 4 month standard used in the SEER database. To ascertain the result, we will first call patients' physicians to determine whether surgery occurred within the designated time frame. Given the possibility that individual patients could seek other opinions and receive surgical care elsewhere, when appropriate, we will ask the patient, or a family member (if the patient is dead or unavailable), whether surgery was performed by someone other than the index physician. If surgery has not occurred, we will ask for reasons. Through appropriate consent, we will retain the option of confirmatory medical records review. For secondary analyses, we will record surgeries that occur beyond the 4 month threshold.

Secondary Outcomes.

1. One year, post-enrollment survival in surgical and non-surgical groups
2. Satisfaction of patients that received interventions compared to those who did not
3. Patients' perceptions of communication for those patients that received intervention compared to those who did not
4. SF-12 scores at baseline, 6 months post-enrollment and 12 months post enrollment

6. Data Analysis:

Our current plan includes:

Descriptive statistics (means, standard deviations, frequencies, proportions, correlations, and graphical displays) will be computed for all study variables at baseline and post-baseline. The distribution of all outcome variables will be assessed to determine if distributional assumptions are valid. Descriptive statistics will be obtained for all the variables overall and by race and site. Statistical methods for addressing each of the specific aims of the study are detailed in this section. Since several statistical tests are planned, there is the possibility of incurring spurious results if we do not correct for multiple comparisons. All tests are based on a 2-sided alpha of 0.05.

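### The 80% power in SAP section 7 treats the historical surgery rate as known; the before/after chi-square the SAP describes has about 47–55% power for the same 6-point gain if the chart baseline is 0.63

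*SAP*

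**What the plan says.** SAP section 7 fixes the sample by budget, patient availability and duration ("The project anticipates enrolling 496 patients into the study") and works back to a detectable difference: "we compute the minimal effect size we can detect with statistical power of 80% for our primary aim, AIM 1". The comparator is the earlier cohort; the outcome is the surgery probability in all patients "as compared to the probability for all patients in the previous study because all groups will receive the data registry and feedback interventions".

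The calculation reads: "Using a one-sample test of proportion with 496 subjects overall and significance level of 0.05, we have 80% power" for 0.63 to 0.69. The same method is applied by race. For Black patients, "With a sample size of 159 for blacks, we have 80% power to detect an overall increase from" 0.55 to 0.66; for 337 White patients the step is 0.66 to 0.73. SAP section 6 sets the error rate: "All tests are based on a 2-sided alpha of 0.05".

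The before/after test itself appears in SAP section 6, in the text under hypothesis 1b: "Cumulative pre-intervention surgical rates will be compared at all sites with post-intervention rates using Pearson's chi-square test". Protocol section D makes the 2008–2009 chart review the baseline for surgical rates and gives its expected size: "We anticipate the availability of approximately 100-150 charts per site in the 2-year pre-study window". With 4 sites that is 400–600 charts.

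Two further before/after analyses matter here. Protocol section E compares control-group surgery rates with historical controls at each site. For hypotheses 2a and 2b, the SAP fits logistic growth models, once in the communicator control group alone and once in all enrollees with a term for the communicator.

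**The concern.** A one-sample test assigns no sampling error to the historical rate. The chi-square in section 6 compares two estimated proportions, and a baseline of 400–600 charts carries about as much error as 496 prospective patients. The printed 80% is therefore not a property of the test that is described.

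Section 7 holds the only power statement in the plan. A reader would take a non-significant before/after result as an adequately powered negative, when on the section's own rates a true 6-point gain would be missed about half the time.

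**Working it through.** **Inputs.** Two-sided alpha 0.05 (SAP section 6). Prospective patients 496, of whom 159 Black and 337 White, with rates 0.63→0.69, 0.55→0.66 and 0.66→0.73 (SAP section 7). Baseline charts 400–600 (protocol section D: 100–150 × 4 sites). The documents give no Black share for the charts. I assume 20%, from the 2007 table in protocol section C (66/327 = 20.2%), and show 30% as an alternative. Clustering is ignored, as in section 7.

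**Step 1: reproduce the printed figure.** One-sample power = Φ[(d − 1.96·s0)/s1], with d = p1 − p0, s0 = √(p0(1−p0)/n) and s1 = √(p1(1−p1)/n).

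- Overall: s0 = 0.02168, s1 = 0.02077; (0.06 − 1.96×0.02168)/0.02077 = 0.843; power 80.0%.
- Black: s0 = 0.03945, s1 = 0.03757; argument 0.870; power 80.8%.
- White: s0 = 0.02580, s1 = 0.02418; argument 0.803; power 78.9%.

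All three match the printed 80% within about a point. A one-sided alpha would give 87–89%, so the section used a two-sided test.

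**Step 2: the two-sample chi-square.** With n0 charts and n1 prospective patients, power = Φ[(d − 1.96·S0)/S1]. Here S0 = √(p̄(1−p̄)(1/n0 + 1/n1)), p̄ is the pooled rate, and S1 = √(p0(1−p0)/n0 + p1(1−p1)/n1).

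- Overall, 400 charts: p̄ = 0.6632, S0 = 0.03176, S1 = 0.03184; argument −0.071; power 47.2%.
- Overall, 600 charts: p̄ = 0.6572, S0 = 0.02881, S1 = 0.02863; argument 0.124; power 54.9%.

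| Comparison | Charts | Power |
|---|---|---|
| Overall, 0.63→0.69, n1 = 496 | 400 / 500 / 600 | 47.2 / 51.5 / 54.9% |
| Black, 0.55→0.66, n1 = 159, 20% share | 81 / 121 | 38.4 / 46.5% |
| Black, 30% share | 120 / 180 | 46.3 / 54.2% |
| White, 0.66→0.73, n1 = 337, 20% Black share | 319 / 479 | 49.5 / 56.7% |
| White, 30% Black share | 280 / 420 | 47.1 / 54.5% |

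The rows by race apply the same test within race. The SAP's own race-specific before/after contrasts use the growth models, which also estimate both proportions. More charts cannot lift the overall figure above the one-sample value, which is its limit as the baseline grows.

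**Step 3: rates detectable with 80% power.** Solving the step 2 formula for p1 gives 0.718 (400 charts) to 0.710 (600) overall. At a 20% Black share it gives 0.731 to 0.712 in Black patients and 0.759 to 0.751 in White patients.

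**Step 4: a different chart baseline.** The case-weighted surgery rate in the protocol section C table is (63×70 + 141×69 + 57×74 + 66×75)/327 = 71.3%. From that baseline the overall detectable rate is 0.794 (400 charts) to 0.787 (600).

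**Step 5: control group only.** The allocation ratio is not stated. Assuming 1:1, 496/2 = 248 controls. For 0.63→0.69, power is 34.3% with 400 charts and 38.1% with 600; 80% power needs a rate of about 0.73–0.74.

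**The case against.** The strongest reply is that section 7 names the previous study, not the charts, as its comparator, so putting the charts beside 0.63 mixes two sources. That stands as a condition on the numbers. Protocol section C says registry data limited to tissue-proven cases overstate the surgery rate, and charts found through billing codes may share that feature, so their baseline could be nearer 71% than 63%. It does not rescue the 80%: the previous study's rates are also estimates, and the size of that study is not given.

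A reader might infer that no analysis in the SAP uses a one-sample test. That is too strong. Directly after the chi-square, the SAP mentions comparing post-intervention rates by a test of proportions without saying against what, and this could be read either way.

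A reader might also infer an inflated false-positive rate, from an analyst entering the chart rate as a constant. No section plans that, and for the constant section 7 does use, the inflation cannot be computed.

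Nor should the 47–55% be read as the power to judge the registry and feedback. Those are hypotheses 2a and 2b, analysed by growth models, and pooling all 496 patients mixes in any communicator effect. The closer simple figure is the control-group one in step 5.

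Finally, 496 was set by budget and availability, so a better calculation changes no enrolment. That is true, and it limits the consequence to what the plan may claim.

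**Conclusion.** The concern holds as a mismatch of method; there is no slip of arithmetic, since the printed figures reproduce for the test named. For the chi-square described, and if the chart baseline equals the previous study's rates, power is about 47–55% overall. At a 20% Black share of charts it is about 38–47% in Black and 50–57% in White patients; at 30%, about 46–54% and 47.1–54.5%. The detectable overall rate is about 0.71–0.72 in place of 0.69, or about 0.79 from a 71% baseline. At a 20% Black share, the detectable rates by race are about 0.71–0.73 (Black) and 0.75–0.76 (White), against the printed 0.66 and 0.73. The control-group comparison has about 34–38% power with 248 controls.

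Slightly higher ceilings of 56% overall and 48% in Black patients might be inferred by doubling the 2007 registry count (2 × 327 = 654 charts). Protocol section D's own figure stops at 600.

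None of these figures is the power of the randomised comparison in hypothesis 1a. Section 7 claims power for Aim 1 but gives none for that comparison, which is a separate gap.

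**What to change.** In SAP section 7:

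- Replace the one-sample calculation with the two-sample calculation that matches the chi-square in section 6, overall and by race.
- Label it as the before/after contrast, and say that it is not the power of the randomised comparison in hypothesis 1a.
- State the assumed chart counts, Black and White shares and baseline rates, including a baseline near 71%.
- Give the corresponding figure for the control-group comparison, with the assumed number of controls.
- Update every figure with the actual chart counts and rates. The chart review falls in the first six months and sites recruit by the start of month 13, so this can be done before recruitment.

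The cost is a recalculation and rewording of one section. No patients or data are added and enrolment stays at 496. The price is a less favourable statement: lower power for the printed differences, or an overall detectable gain of about 8–9 points (0.71–0.72 less 0.63) where 6 is now claimed.
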